**Table 2: Dosing for Subjects  $\geq 40$  kg (on an mg/hour basis)**

Days	Start Time from Study Drug Initiation	Study Drug Dose (mg/hour)	Study Drug Infusion Rate (mL/hour)	Duration
Day 1	0 hours: bolus dose via syringe or infusion pump	30	30	3 minutes
Day 1	0 hours through 2 hours post study drug initiation: continuous infusion, started with bolus	80	80	2 hours
Day 1	2 hours through 12 hours post study drug initiation	40	40	10 hours
Day 1	12 hours through 24 hours post study drug initiation	20	20	12 hours
Day 2 a	24 hours through 36 hours post study drug initiation	20 - 45	20 - 45	12 hours
Study Drug Taper				
Day 2 b	36 through 48 hours post study drug initiation (12-hour taper)	13.34 - 30.02	13.34 - 30.02	4 hours
		8.90 - 20.02	8.90 - 20.02	4 hours
		5.93 - 13.35	5.93 - 13.35	4 hours

a. On Day 2 (24-36 hours), the continuous infusion rate can be increased from 20 mg/hour to a maximum rate of 45 mg/hour at any time, if needed, to manage seizure relapse or other medical reason.

b. To taper the study drug, the infusion rate at the 36-hour post study drug initiation timepoint will be reduced by 33.3% every 4 hours until the infusion rate is stopped or if the infusion rate becomes too low to sustain the infusion line, at which point it will be stopped. The first taper will be 33.3% from the current infusion rate, the second taper will be 33.3% from the first tapered infusion rate, and the final taper will be 33.3% from the previous tapered infusion rate. If, per the investigator's judgment, the study drug taper needs to start at an earlier timepoint during the treatment period, the infusion rate at the start of the first taper will be decreased by 33.3% every 4 hours as described.

Subjects weighing  $< 40$  kg will be dosed on a per-kilogram basis:

- A 0.43-mg/kg bolus dose (over ~3 minutes) will be administered with a continuous infusion at a dose of 1.14 mg/kg/hour for 2 hours followed by a continuous infusion rate of 0.57 mg/kg/hour for 10 hours, and 0.29 mg/kg/hour for the remaining 12 hours of Day 1.
- On Day 2 (24-36 hours) the continuous infusion dose of 0.29 mg/kg/hour will continue until the start of the study drug taper at 36 hours post study drug initiation. If needed, to manage seizure relapse or for another medical reason, the infusion dose can be increased from 0.29 mg/kg/hour up to a maximum of 0.64 mg/kg/hour at any time during hours 24-36 of Day 2.
- To taper the study drug, the infusion rate at the 36-hour post study drug initiation timepoint will be reduced by 33.3% every 4 hours until the infusion is stopped or if the infusion rate becomes too low to sustain the infusion line, at which point it will be stopped. The first taper

will be 33.3% from the current infusion rate, the second taper will be 33.3% from the first tapered infusion rate, and the final taper will be 33.3% from the previous tapered infusion rate. If, per the investigator's judgment, the study drug taper needs to start at an earlier timepoint during the treatment period, the infusion rate at the start of the first taper will be decreased by 33.3% every 4 hours as described.

- At the time the study drug infusion is discontinued the subject will progress to the in-patient follow-up day assessments/procedures.

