j. EEG is required for confirmation of NCSE diagnosis. Continuous EEG recording ideally should start before study drug initiation and continue through the in-patient follow-up day. If continuous EEG is not possible or needed to diagnose (for convulsive SE) it should be instituted at the earliest possible time after study drug initiation (if a pre-dose EEG was not performed for the diagnosis of convulsive SE).

k. Subjects will receive a 30 mg bolus (over ~3 minutes) with a continuous infusion at a rate of 20-80 mg/hour for approximately 36 hours followed by 12-hour taper.

l. Blood sample collection for pharmacokinetic analysis (venous or arterial) will occur at 60-minutes then at 2-,4-,8-,10-, 24- and 36-hours after the start of study drug infusion. Collect at the time of study drug discontinuation, either at the end of the study drug taper or if the study drug administration is stopped without a taper and 24-hours after study drug discontinuation. After the initial SE cessation, collect a sample at the first instance of seizure activity or SE relapse and the subject does not progress to an IV anesthetic. Between study drug initiation and the in-patient follow-up day, where possible, collect a sample if the decision is made to intubate the subject; collect at the time of introduction of a new IV AED for safety/efficacy (not for AEDs given prophylactically for "transition/bridging"), and at the time of any serious adverse event (related or not related). PK samples cannot be collected from the study drug infusion line. The location of study drug access and location of PK sample collection should be documented in the subject's source.

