### Quantitative Composition of Ganaxolone IV Solution, 1 mg/mL – 100 mL/Vial

Component	Reference to Standards	Content per mL (mg/mL)	Concentration (%w/w)	Function
Ganaxolone	Marinus	1.00	0.097	Active ingredient
Betadex sulfobutyl ether sodium (Captisol)	NF	59.74	5.817	Solubilizing agent
Potassium phosphate, monobasic (KH 2 PO 4 )	NF	2.46	0.239	Buffer agent a
Sodium phosphate, dibasic heptahydrate (Na 2 HPO 4 .7H 2 O)	USP	2.78	0.271	Buffer agent a
Sodium chloride	USP	2.00	0.195	Tonicity modifying agent
Water for injection	USP	q.s. 1 mL	93.381	Diluent

NF = National Formulary; USP = United States Pharmacopeia; w/w = weight by weight.

a Formulation pH = 6.4

**Drug Product Name:** Ganaxolone IV Solution, 1 mg/mL – 100 mL/vial

**Manufacturer:** Alliance Contract Pharma, LLC., Harleysville, PA 19438 USA

**Strength for Open-Label Group:** ready-to-infuse 1-mg/mL sterile solution in a glass vial

**Packaging:** Ganaxolone IV Solution, 1 mg/mL – 100 mL/vial will be provided to the site as individual vials containing 1 mg/mL of Ganaxolone.

Changes to sponsor-supplied packaging prior to dosing may not occur without full agreement in advance by the sponsor.

**Storage:** The investigator has the overall responsibility for ensuring that study drug is stored in a secure, limited-access location. Limited responsibility may be delegated to the pharmacy or member of the study team, but this delegation must be documented. Study drugs are distributed by the pharmacy or by a nominated member of the study team.

Ganaxolone IV solution, 1 mg/mL – 100 mL/vial has on-going stability and to date has been found stable if stored at 15°-25°C (59°-77°F) until use. Excursions up to 30°C (86°C) that are experienced in pharmacies, hospitals, and warehouses, and during shipping are allowed.

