### **6.2.3 Dosing**

Total adjunctive ganaxolone IV solution therapy infusion treatment is planned to be 2 days which includes a 12-hour study drug taper. All subjects will have an ~3-minute bolus dose with a continuous infusion at the rate of 20-80 mg/hour, and a 12-hour study drug taper (see Table 2 and 3 for details). Once study drug administration is started it should be delivered for 2 days (48 hours) which includes a 12-hour taper.

Study drug should be administered, ideally, through a dedicated (peripheral or central) IV line. These infusion parameters result in daily doses of ganaxolone of  $\leq$  830 mg/day and Captisol of  $\leq$  50 g/day as agreed upon with the FDA. Based on PK modeling, it is predicted that maximum concentrations of ganaxolone should remain within 1,000 ng/mL during infusion, but some variability is expected due to, for example, differences in subjects' weight. Note, at any time, the infusion rate of the ongoing administration may be decreased for safety reasons, see Dose Adjustments and Interruptions section below for more information.

Note, pharmacokinetic data from study 1042-0405 in healthy volunteers showed that a bolus infusion of 30 mg ganaxolone over 5 minutes led to transient peak concentration levels ( $C_{max}$ ) above 1,000 ng/mL (maximal observed  $C_{max}$  was 1,850 ng/mL) with no safety concerns. Infusion of 30 mg/hour for 1 hour and 20 mg/hour for 4 hours led to concentrations of 258 and 215 ng/mL, respectively, again without any safety concerns (see Section 1.2 Product Background and Clinical Information).

During the open-label group, based on the safety, efficacy, and pharmacokinetic data from the ongoing study, the infusion parameters in subsequent subjects may be adjusted to maximize the safety and efficacy of study subjects. If the infusion parameters are amended, the new infusion parameters will not exceed the daily limit of 50 g/day Captisol ( $\leq$  830 mg/day ganaxolone) as agreed upon with the FDA. The revised infusion parameters will be communicated to Clinical Sites in a Protocol Administrative Change Memo and kept in the study and site files.

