Potential subjects must have failed one 2nd line IV AED therapy, administered at an appropriate dose and duration to show efficacy. Ganaxolone IV solution (open-label group) or ganaxolone IV solution or placebo (double-blind group) will be administered in combination with standard of care at the time that the first 2nd line IV AED has failed and the second 2nd line AED is medically indicated during the treatment of SE. Study drug must be administered with 2nd line IV AED treatment and should be initiated as close to the dose initiation of the second 2nd line IV AED as possible.

Upon administration of study drug, subjects will be monitored for improvement or resolution of SE (clinical or EEG response).

Note, the infusion rate cannot be rounded-up regardless whether dosing is in subjects  $\geq 40$  kg or  $< 40$  kg.

Subjects weighing at least 40 kg:

- A 30-mg bolus dose (over ~3 minutes) will be administered with a continuous infusion of 80 mg/hour for 2 hours followed by a continuous infusion rate of 40 mg/hour for 10 hours, and then 20 mg/hour for the remaining 12 hours of Day 1.
- On Day 2 (24-36 hours) the continuous infusion rate of 20 mg/hour will continue until the start of the study drug taper at 36 hours post study drug initiation. If needed, to manage seizure relapse or another medical reason, the infusion rate can be increased from 20 mg/hour up to a maximum rate of 45 mg/hour at any time during hours 24-36 of Day 2.
- To taper the study drug, the infusion rate at the 36-hour post study drug initiation timepoint will be reduced by 33.3% every 4 hours until the infusion is stopped or if the infusion rate becomes too low to sustain the infusion line, at which point it will be stopped. The first taper will be 33.3% from the current infusion rate, the second taper will be 33.3% from the first tapered infusion rate, and the final taper will be 33.3% from the previous tapered infusion rate. If, per the investigator's judgment, the study drug taper needs to start at an earlier timepoint during the treatment period, the infusion rate at the start of the first taper will be decreased by 33.3% every 4 hours as described.
- At the time the study drug infusion is discontinued the subject will progress to the in-patient follow-up day assessments/procedures.

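### The bolus rows of protocol Tables 2 and 3 carry per-hour units, so Table 2 prints a bolus pump rate 20 times too low

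*Protocol*

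**What the plan says.** For subjects of at least 40 kg, Section 6.2.3 orders: "A 30-mg bolus dose (over ~3 minutes) will be administered with a continuous infusion of 80 mg/hour for 2 hours". The Synopsis and footnote k of Table 1 also give 30 mg as an amount over about 3 minutes. For subjects under 40 kg, the Synopsis and Section 6.2.3 order 0.43 mg/kg over about 3 minutes.

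Table 2 is titled and headed on a per-hour basis. Its first row, "0 hours: bolus dose via syringe or infusion pump", shows 30 in the dose column (mg/hour), 30 in the rate column (mL/hour) and 3 minutes as the duration. The next row, "0 hours through 2 hours post study drug initiation: continuous infusion, started with bolus", shows 80 in both columns for 2 hours.

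Table 3 is laid out in mg/kg/hr, and its bolus row shows 0.43 for 3 minutes. Its rate cell says only that the rate depends on weight, and footnote a refers to the Pharmacy Manual.

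The footnotes to the two tables deal with Day 2 rates, the taper and, in Table 3, the Pharmacy Manual. None exempts the bolus row from the column units. Section 6.1 describes the open-label product as a "ready-to-infuse 1-mg/mL sterile solution in a glass vial".

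**The concern.** Each bolus row puts a total amount under a per-hour heading. Read as labelled, the bolus is one-twentieth of the ordered dose.

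This matters more than a slip in background text. Section 6.2.3 sends the reader to these tables for the regimen ("see Table 2 and 3 for details"), and the row allows an infusion pump. A pump is set in mL/hour, and the only figure Table 2 prints under that heading is wrong. The figures do not stand out either: 30.02 mL/hour is a genuine taper rate in Table 2, and 0.43 also appears in Table 3 as a genuine mg/kg/hr rate at the first taper step. Section 6.2.3 also forbids rounding rates up or exceeding those specified, so a cautious user would not readily move from 30 to 600.

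The protocol itself treats amount and rate as different regimens. For healthy volunteers it reports a 30 mg bolus over 5 minutes with peaks above 1,000 ng/mL, and separately: "Infusion of 30 mg/hour for 1 hour and 20 mg/hour for 4 hours led to concentrations of 258 and 215 ng/mL, respectively". Those volunteers had no concurrent 80 mg/hour infusion, so the figures do not predict levels in this trial. They show only that the unit is not cosmetic.

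At stake is the early exposure the bolus is meant to give. The first scheduled status epilepticus assessment is 15 minutes after study drug initiation.

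**Working it through.** **Inputs**
- Ordered bolus: 30 mg, or 0.43 mg/kg, over about 3 minutes (Section 6.2.3 text).
- Table 2 bolus row: 30 mg/hour, 30 mL/hour, 3 minutes. Table 3 bolus row: 0.43 mg/kg/hr, 3 minutes.
- Day 1 infusion, at least 40 kg: 80 mg/hour for 2 h, 40 for 10 h, 20 for 12 h. Under 40 kg: 1.14, 0.57 and 0.29 mg/kg/hour for the same durations.
- Concentration 1 mg/mL; Captisol 59.74 mg/mL (Section 6.1 composition table).
- Stated limits: 830 mg/day ganaxolone, 50 g/day Captisol.

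**1. Reproduce the stated daily dose**
- Infusion: 80 x 2 + 40 x 10 + 20 x 12 = 160 + 400 + 240 = 800 mg.
- With a 30 mg bolus: 800 + 30 = 830 mg, exactly the stated figure. Captisol: 830 mL x 59.74 mg/mL = 49.58 g, under 50 g.
- The three Day 1 infusion rows therefore work as rate x duration. Only the bolus row does not.

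**2. Bolus rows read as labelled**
- Table 2: 30 mL/h x 3/60 h x 1 mg/mL = 1.5 mg; 30/1.5 = 20.
- Table 3: 0.43 x 3/60 = 0.0215 mg/kg; 0.43/0.0215 = 20.
- Day 1 total with a 1.5 mg bolus: 801.5 mg (Captisol 47.88 g), which does not match 830 mg.

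**3. Rates that deliver the ordered dose in 3 minutes**
- 30 mg / (3/60 h) = 600 mg/hour = 600 mL/hour.
- 0.43 / (3/60) = 8.6 mg/kg/hour.

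**4. Size if Table 2 were followed literally (30 mL/hour, stopped at 3 minutes)**

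The infusion is the same in both readings, so the shortfall stays at 30 - 1.5 = 28.5 mg once the 3 minutes end.

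| Time | As labelled (mg) | As ordered (mg) | Shortfall |
|---|---|---|---|
| 3 min | 1.5 + 4 = 5.5 | 30 + 4 = 34 | 84% |
| 15 min | 1.5 + 20 = 21.5 | 30 + 20 = 50 | 57% |
| 24 h | 801.5 | 830 | 3.4% |

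For subjects under 40 kg the shortfall would be 0.43 - 0.0215 = 0.4085 mg/kg, with nearly the same percentages: 0.4085/0.487 = 83.9%, 0.4085/0.715 = 57.1% and 0.4085/11.89 = 3.4%.

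**The case against.** The case against giving this much weight is substantial.

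- **The dose is settled elsewhere.** The text beside each table gives the right amount, and the 830 mg total confirms it. This stands: it is a labelling error, and nothing in the regimen is ambiguous.
- **The row signals its own meaning.** It is called a bolus, names a syringe first, and would run slower than the 80 mL/hour infusion started with it. This lowers the chance of literal use but does not make the printed rate right.
- **The shortfall depends on how the pump is used.** If 30 mL were set to run at 30 mL/hour, the full 30 mg would go in over 1 hour. At 15 minutes the subject would have 7.5 + 20 = 27.5 mg against 50 mg (45% short), and the gap would close by 1 hour. The arithmetic is correct, but this reading ignores the 3-minute duration in the same row, and it still turns a 3-minute bolus into an hour-long infusion.
- **The Pharmacy Manual may have it right.** Section 6.2.3 and the open-label vial label send sites to it. It is not among the documents, so it can be neither credited nor faulted.
- **Table 3 is the weaker half.** It prints no wrong pump rate, only a wrong unit on the dose.
- **The error may not have touched any analysed subject.** The SAP is written to protocol Amendment 3, with a 25 mg bolus (Appendix 1, footnote n) and cohorts targeted at 713, 650 and 500 mg/day, and it says the study closed before the double-blind phase. This stands, and it limits what can be claimed.

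**Conclusion.** The concern holds. Both bolus rows are wrong as written, by a factor of 20, and Table 2 also prints a wrong pump rate: 30 mL/hour where 600 mL/hour is needed. The intended dose is clear, so the fault is in the units, not the regimen.

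The 28.5 mg shortfall is hypothetical. It assumes a pump set to the printed rate and stopped at the printed 3 minutes, with drug at 1 mg/mL. On that assumption the effect is concentrated in the first minutes and small by 24 hours. No daily limit is breached on either reading, no misdosing is shown, and no analysis is affected. The tables are nevertheless working dosing instructions, so the rows should be corrected.

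**What to change.** - Table 2 bolus row: state 30 mg in total (30 mL) over about 3 minutes.
- Table 3 bolus row: state 0.43 mg/kg in total over about 3 minutes.
- Add a footnote to both tables that the per-hour headings do not apply to the bolus row.
- Leave the bolus rate cell blank. If a rate is wanted, print 600 mL/hour in Table 2, or the equivalent of 8.6 mg/kg/hour in Table 3, and only after checking it against the Pharmacy Manual.

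Issue this as a clarification memo or amendment. Because the double-blind phase moves to a separate phase 3 study, the more useful step is to carry the corrected rows into any later protocol that reuses these tables.

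The cost is two table rows, one footnote and one check of the Pharmacy Manual. Dose, design and analysis do not change.

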**Table 3: Dosing for Subjects < 40 kg (on an mg/kg/hour basis)**

Days	Start Time from Study Drug Initiation	Study Drug Dose (mg/kg/hr)	Study Drug Infusion Rate (mL/hr) a	Duration
Day 1	0 hours: bolus dose via syringe or infusion pump	0.43	Variable depending on subject's weight	3 minutes
Day 1	0 hours through 2 hours post study drug initiation dose: continuous infusion, started with bolus	1.14	Variable	2 hours
Day 1	2 hours through 12 hours post study drug initiation	0.57	Variable	10 hours
Day 1	12 hours through 24 hours post study drug initiation	0.29	Variable	12 hours
Day 2 b	24 hours through 36 hours post study drug initiation	0.29 - 0.64	Variable	12 hours
Study Drug Taper				
Day 2 c	36 through 48 hours post study drug initiation (12-hour taper)	0.19 - 0.43	Variable	4 hours
		0.13 - 0.29	Variable	4 hours
		0.08 - 0.19	Variable	4 hours

a. Reference the Pharmacy Manual for study drug infusion rates based on mg/kg/hour dosing.

b. On Day 2 (24-36 hours), the continuous infusion dose can be increased from 0.29 mg/kg/hour to a maximum dose of 0.64 mg/kg/hour at any time, if needed, to manage seizure relapse or other medical reason.

c. To taper the study drug, the infusion rate at the 36-hour post study drug initiation timepoint will be reduced by 33.3% every 4 hours until the infusion rate becomes too low to sustain the infusion line, at which point it will be stopped. The first taper will be 33.3% from the current infusion rate, the second taper will be 33.3% from the first tapered infusion rate, and the final taper will be 33.3% from the previous tapered infusion rate. If, per the investigator's judgment, the study drug taper needs to start at an earlier timepoint during the treatment period, the infusion rate at the start of the first taper will be decreased by 33.3% every 4 hours as described.

### Medical Oversight:

Medical personnel must be present at all times during at least the first 3 hours after the start of the study drug infusion. Then close monitoring of the subject by the study staff will continue as medically needed throughout the study.

### New AED Introduction:

- For the first 10-hours of study drug administration the decision to initiate new IV AEDs should be based on safety or efficacy and confirmed by relapsing clinical presentation or electrographic activity. Initiation of any new AEDs prophylactically (so called “transition/bridging”) is not recommended, unless medically indicated.
- In the event of safety or efficacy presentation, i.e. seizure relapse that would prompt the investigator to make a treatment intervention, introduction of a new IV AED is recommended over immediate progression to a 3rd line agent, however all treatment decisions are at the investigator’s discretion.
- After the first 10-hours investigators are encouraged to initiate prophylactic AEDs in anticipation of the study drug taper at 36 hours post study drug initiation on Day 2.

### Scenarios for stopping the study drug without a taper include:

- For subjects who receive study drug for less than 2 hours and/or
- Study drug infusion is discontinued or interrupted, and the decision is made to not restart the infusion and/or
- If at any time during study drug administration the subject progresses to an IV anesthetic drug (a 3rd line and/or 4th line treatment) for seizure suppression or
- It is no longer safe to continue drug administration per the investigator’s medical judgment.

### Dose Optimization:

During the open-label group, based on the safety, efficacy, and pharmacokinetic data from the ongoing study, the infusion parameters in subsequent subjects may be adjusted to maximize the safety and efficacy of study subjects. If the infusion parameters are amended, the new infusion parameters will not exceed the daily limit of 50 g/day Captisol ( $\leq$  830 mg/day ganaxolone) as agreed upon with the FDA. The revised infusion parameters will be communicated to Clinical Sites in a Protocol Administrative Change Memo and kept in the study and site files.

For study drug dosing instructions reference the Pharmacy Manual.

### Dose Adjustments and Interruptions:

Dose (infusion rate) decreases and interruptions of the continuous infusion are discouraged at any time during study drug treatment. However, if there is an urgent medical need (e.g., severe hypotension, acidosis, severe sedation) or a subject’s standard of care requires they undergo a

procedure for which the infusion would need to be decreased or interrupted (e.g., an MRI scan) it should be kept as short as possible but no longer than 6 hours. If > 6 hours the Marinus Medical Monitor must approve the re-start of the infusion.

Note:

- After the dose (infusion rate) decrease or infusion interruption, it will be per the investigator's judgment and assessment of risk/benefit if the subject should continue in the study or early discontinue.
- In cases when severe sedation is seen and early drug discontinuation is being considered, the Marinus Medical Monitor should be contacted prior to infusion termination, if feasible.
- If the decision is made for the subject to continue in the study, the infusion should be restarted at the rate matching the rate at the corresponding nominal time, counted from the beginning of the study drug infusion on Day 1. A study drug bolus or "catch-up" dose to deliver the study drug that was missed during the interruption should not be administered.
- Dose (infusion rate) increases above those specified in the protocol (or based on a future Protocol Administrative Change Memo) are not allowed at any time during infusion. This is to ensure daily Captisol and ganaxolone limits are kept  $\leq$  50 g/day and  $\leq$  830 mg/day, respectively.

